### **6.5.3. Sensitivity Analysis**

Sensitivity analysis for these efficacy endpoints may be performed with the same methods described above based on the FAS, and with cases counted starting at different time points as applicable.

For the sensitivity analysis of efficacy endpoints in the long-term analysis and booster dose analysis, in addition to the efficacy endpoint COVID-19 (CDC Case Definition) and secondary case (P301 Primary Definition) COVID-19 based on eligible symptoms and confirmed positive RT-PCR results (central lab or local diagnostic test) originally defined in SAP, a sensitivity analysis using efficacy endpoint COVID-19 (CDC Case Definition) and secondary case (P301 Primary Definition) COVID-19 based on both RT-PCR results and other COVID-19 test results including home antigen tests will also be derived.

Specifically, each COVID-19 case will be based on eligible symptom(s) and all positive COVID-19 test results including RT-PCR (central lab or local diagnostic test) and (home) antigen test results (refer to section 6.5.1. for the derivation of COVID-19 cases in SAP for Part 1 open-label phase and Part 2 blinded phase)

### **6.5.4. Exploratory Analysis of SARS-CoV-2 Exposure and Symptoms**

SARS-CoV-2 reported exposure history and symptoms assessment will be assessed during the study.

SARS-CoV-2 reported exposure history and symptoms assessment will be provided in a listing for Part 2 Open-label Phase and booster dose Analysis separately as applicable.

## **6.6. Interim Analysis**

Please refer to SAP for Part 1 open-label phase and Part 2 blinded phase

## **6.7. Final Analysis**

The final analysis of all applicable endpoints will be performed after all participants have completed all planned study procedures. Results of this analysis will be presented in a final CSR, including individual listings.

## 8. List of Appendices

### 8.1. Appendix A Standards for Safety and Immunogenicity Variable Display in TFLs

**Continuous Variables:** The precision for continuous variables will be based on the precision of the data itself. The mean and median will be presented to one decimal place more than the original results; the SD will be presented to two decimal places more than the original results; the minimum and maximum will be presented to the same precision as the original results.

**Categorical Variables:** Percentages will be presented to 1 decimal place.

### 8.2. Appendix B Analysis Visit Windows for Safety and Immunogenicity Analysis

Safety and Immunogenicity Analysis will be summarized using the following analysis visit window for post injection assessments:

Step 1: If the safety and immunogenicity assessments are collected at scheduled visit, i.e. nominal scheduled visit, the data collected at scheduled visit will be used.

Step 2: If the safety and immunogenicity assessments are not collected at the scheduled visit, assessments collected at unscheduled visit will be used using the analysis visit windows described in Table 4 below.

If a subject has multiple assessments within the same analysis visit, the following rule will be used:

- If multiple assessments occur within a given analysis visit, the assessment closest to the target study day will be used.
- If there are 2 or more assessments equal distance to the target study day, the last assessment will be used.

**Table 4. Visit Window**

| Visit   | Target Study Day | Visit Window in Study Day |
|---|------------------|---------------------------|
| Nasal Swabs for SARS-CoV-2 for Part 1 and Part 2 Booster mRNA-1273 Dose: |                  |                           |

|   |   |                                |
|---|---|--------------------------------|
| BD-Day 1  | 1 (Date of Injection in booster dose Analysis) relative to BD-Day 1 | $\leq 1$ and VISIT is BD-Day 1 |
| BD-Day 29   | 29 relative to BD-Day 1   | [2, 105]                       |
| BD-Day 181  | 181 relative to BD-Day 1  | $\geq 106$                     |
|   |   |                                |
| Nasal Swabs for SARS-CoV-2 for Part 3 First Two Doses of Primary Series: |   |                                |
| Day 1   | 1 (Date of First Injection)   | 1, Pre-first-dose              |
| Day 29 (Month 1)  | 29 (Date of Second Injection)                                       | [2, 43]                        |
| Day 57 (Month 2)  | 57  | $\geq 44$                      |
|   |   |                                |
| Nasal Swabs for SARS-CoV-2 for Part 3 Third Dose:                        |   |                                |
| BD-Day 1 (Month 5)  | 1 (Date of Injection in Thrid Dose Analysis) relative to BD-Day 1   | $\leq 1$ and VISIT is BD-Day 1 |
| BD-Day 29 (Month 6)   | 29 relative to BD-Day 1   | [2, 105]                       |
| BD-Day 181 (Month 11)   | 181 relative to BD-Day 1  | [106, 274]                     |
| BD-Day 366 (Month 17)   | 366 relative to BD-Day 1  | $\geq 275$                     |
|   |   |                                |
| Immunogenicity for Part 1 and Part 2 Booster mRNA-1273 Dose:             |   |                                |
| BD-Day 1  | 1 (Date of Injection in Booster dose Analysis) relative to BD-Day 1 | $\leq 1$ and VISIT is BD-Day 1 |
| BD-Day 29   | 29 relative to BD-Day 1   | [2, 105]                       |
| BD-Day 181  | 181 relative to BD-Day 1  | [106, 274]                     |
| BD-Day 366  | 366 relative to BD-Day 1  | $\geq 275$                     |
|   |   |                                |
| Immunogenicity for Part 3 First Two Doses of Primary Series:             |   |                                |
| Day 1   | 1 (Date of First Injection)   | 1, Pre-first-dose              |
| Day 57 (Month 2)  | 57  | [44,133]                       |
|   |   |                                |
| Immunogenicity for Part 3 Third Dose:                                    |   |                                |
| BD-Day 1 (Month 5)  | 1 (Date of Injection in Booster dose Analysis) relative to BD-Day 1 | $\leq 1$ and VISIT is BD-Day 1 |

|                       |                          |            |
|-----------------------|--------------------------|------------|
| BD-Day 29 (Month 6)   | 29 relative to BD-Day 1  | [2, 105]   |
| BD-Day 181 (Month 11) | 181 relative to BD-Day 1 | [106, 274] |
| BD-Day 366 (Month 17) | 366 relative to BD-Day 1 | $\geq 275$ |

### **8.3. Appendix C Imputation Rules for Missing Prior/Concomitant Medications and Non-Study Vaccinations**

Imputation rules for missing or partial medication start/stop dates are defined below:

1. Missing or partial medication start date:

- If only Day is missing, use the first day of the month, unless:
  - The medication end date is after the date of first injection or is missing AND the start month and year of the medication coincide with the start month and year of the first injection. In this case, use the date of first injection
- If Day and Month are both missing, use the first day of the year, unless:
  - The medication end date is after the date of first injection or is missing AND the start year of the medication coincide with the start year of the first injection. In this case, use the date of first injection
- If Day, Month and Year are all missing, the date will not be imputed, but the medication will be treated as though it began prior to the first injection for purposes of determining if status as prior or concomitant.

2. Missing or partial medication stop date:

- If only Day is missing, use the earliest date of (last day of the month, study completion, discontinuation from the study, or death).
- If Day and Month are both missing, use the earliest date of (last day of the year, study completion, discontinuation from the study, or death).
- If Day, Month and Year are all missing, the date will not be imputed, but the medication will be flagged as a continuing medication.

In summary, the prior, concomitant or post categorization of a medication is described in Table 5 below.

**Table 5. Prior, Concomitant, and Post Categorization of Medications and Non-study Vaccinations**

| Medication Start Date                              | Medication Stop Date            |  |   |
|---|--|--|---|
|   | < First Injection Date of IP | ≥ First Injection Date and ≤ 28 Days After Last Injection | ≥ 28 Days After Last Injection [2] |
| < First injection date of IP [1]                          | P                                      | P, C   | P, C, A                                   |
| ≥ First injection date and ≤ 28 days after last injection | -                                      | C  | C, A                                      |
| > 28 days after last injection                            | -                                      | -  | A   |

A: Post; C: Concomitant; P: Prior

[1] includes medications with completely missing start date

[2] includes medications with completely missing end date

#### **8.4. Appendix A Imputation Rules for Missing AE dates**

Imputation rules for missing or partial AE start dates and stop dates are defined below:

1. Missing or partial AE start date:

- If only Day is missing, use the first day of the month, unless:
  - The AE end date is after the date of first injection or is missing AND the start month and year of the AE coincide with the start month and year of the first injection. In this case, use the date and time of first injection, even if time is collected.
- If Day and Month are both missing, use the first day of the year, unless:

- The AE end date is after the date of first injection or is missing AND the start year of the AE coincides with the start year of the first injection. In this case, use the date of first injection
- If Day, Month and Year are all missing, the date will not be imputed. However, if the AE end date is prior to the date of first injection, then the AE will be considered a pre-treatment AE. Otherwise, the AE will be considered treatment-emergent.

2. Missing or partial AE end dates will not be imputed.

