- b) study day on or after the date of the booster/third dose will be calculated as: date of assessment/event – date of the injection in booster/third dose analysis + 1;

**Study day relative to the most recent injection** will be calculated as below:

- a) study day on or after the date of the first injection in Part 2 open-label phase (if applicable) but before the second injection in Part 2 open-label phase (if applicable) will be calculated as: date of assessment/event – date of the first injection of mRNA-1273 in Part 2 open-label phase + 1;
- b) study day on or after the date of the second injection in Part 2 open-label phase (if applicable) but before the injection in booster dose analysis (if applicable) will be calculated as: date of assessment/event – date of the second injection of mRNA-1273 in Part 2 open-label phase + 1;
- c) study day on or after the date of booster/third dose analysis (if applicable) will be calculated as: date of assessment/event – date of the injection in booster/third dose analysis + 1;  
if study day is on the same day as the injection, date and time will be compared with the injection date and time.

**For calculation regarding antibody values in booster/third dose analysis**, antibody values reported as below LLOQ will be replaced by  $0.5 \times \text{LLOQ}$ . Values that are greater than the upper limit of quantification (ULOQ) will be converted to the ULOQ if actual values are not available, and actual values will be used if available. Missing results will not be imputed.

The following analysis periods for Long-term and booster/third dose phase safety analyses will be used as applicable for specific subjects group in this study:

- Up to 28 days after any vaccination (mRNA-1273 primary series or booster/third dose): this stage starts at the day of each vaccination and continue through the earliest date of (the day of each vaccination and 27 subsequent days, next vaccination [if applicable]). This analysis period will be used as the primary analysis period for safety analyses including unsolicited AE, except for solicited AR, unless specified otherwise.
- Overall period or throughout the study: this analysis period starts at the first injection on Day 1 and continues through the earliest date of (study completion, discontinuation from the study, or death).

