### Long-term Analysis (including Part 2 Open-Label Phase)

For unsolicited AE or assessments that will be collected throughout the study after mRNA-1273 primary series, this analysis period starts from the first dose date of mRNA-1273 and continues until the earliest date of (booster dose, study completion, discontinuation from the study, or death).

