### Booster/Third Dose Analysis

For unsolicited AE or assessments that will be collected throughout the study, this analysis period starts from the booster/third dose date and continues until the earliest date of (study completion, discontinuation from the study, or death).

**Unscheduled visits:** Unscheduled visit measurements will be included in analysis as follows:

- In scheduled visit windows per specified visit windowing rules.
- In the derivation of baseline/last on-treatment measurements.
- In the derivation of maximum/minimum on-treatment values and maximum/minimum change from baseline values for safety analyses.
- In individual subject data listings as appropriate.

**Visit windowing rules:** The analysis visit windows for protocol-defined visits are provided in [Appendix B](#).

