### **Incomplete/missing data:**

- Imputation rules for missing prior/concomitant medications, non-study vaccinations and procedures are provided in [Appendix C](#).
- Imputation rules for missing AE dates are provided in [Appendix D](#).
- For laboratory assessments, if majority of results are indefinite, imputation of these values will be considered. If the laboratory results are reported as below the LLOQ (e.g., <0.1), the numeric values will be imputed by  $0.5 \times \text{LLOQ}$  in the summary. If the laboratory results are reported as greater than the ULOQ (e.g., “>3000”), the numeric values will be imputed by ULOQ in the summary.
- Other incomplete/missing data will not be imputed, unless specified otherwise.

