### **Analysis periods**

The following analysis periods and treatment groups will be used for long-term and booster dose analysis.

- Long-term Analysis (Part 1 Open-Label Phase plus Part 2 Blinded and Open-Label Phase, until Booster Dose)

| Group               | Category                    | Start Date                      | End Date  |
|---------------------|-----------------------------|---------------------------------|---|
| mRNA-1273           | Safety                      | Date of First Dose of mRNA-1273 | Earliest date of booster dose (exclusive), study discontinuation, study completion, death, or data cutoff |
| Placebo - mRNA-1273 |                             |                                 | Earliest date of booster dose (inclusive), study discontinuation, study completion, death, or data cutoff |
| mRNA-1273           | Efficacy/
Immunogenicity | Date of First Dose of mRNA-1273 | Earliest date of booster dose (inclusive), study discontinuation, study completion, death, or data cutoff |
| Placebo - mRNA-1273 |                             |                                 | Earliest date of booster dose (inclusive), study discontinuation, study completion, death, or data cutoff |

- Long-term analysis (Part 1 Open-Label Phase plus Part 2 Blinded and Open-Label Phase, Regardless of Booster Dose) incidence rate will also be performed for the entire study period after the first dose of mRNA-1273 regardlesss of booster dose.

| Group               | Category                    | Start Date                      | End Date  |
|---------------------|-----------------------------|---------------------------------|---|
| mRNA-1273           | Safety                      | Date of First Dose of mRNA-1273 | Earliest date of study discontinuation, study completion, death, or data cutoff |
| Placebo - mRNA-1273 |                             |                                 | Earliest date of study discontinuation, study completion, death, or data cutoff |
| mRNA-1273           | Efficacy/
Immunogenicity | Date of First Dose of mRNA-1273 | Earliest date of study discontinuation, study completion, death, or data cutoff |
| Placebo - mRNA-1273 |                             |                                 | Earliest date of study discontinuation, study completion, death, or data cutoff |

- Part 3, First Two Doses of Primary Series Analysis

| Group           | Category | Start Date                      | End Date  |

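### The open-label/booster SAP protects partial AE start dates only around the first injection, so AEs that began after a booster or third dose in the same month are dated before it and leave the post-dose safety tables

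*SAP*

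**What the plan says.** In the open-label/booster SAP, section 6.1 sends the reader to one appendix for AE dates ("Imputation rules for missing AE dates are provided in" Appendix D). That appendix is section 8.4, whose heading is labelled Appendix A. It gives two defaults:

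- "If only Day is missing, use the first day of the month, unless"
- "If Day and Month are both missing, use the first day of the year, unless"

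Each default has one exception. If the AE ended after the first injection, or has no end date, and "the start month and year of the AE coincide with the start month and year of the first injection" (or the years coincide, for year-only dates), the start is set to the first-injection date. No booster, third dose or crossover dose is mentioned. The same rule stands in section 8.4 of the SAP for Part 1 and the Part 2 blinded phase.

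The safety periods in section 6.1 of the open-label/booster SAP open at these points:

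- Booster/third dose: "this analysis period starts from the booster/third dose date and continues until the earliest date of" study completion, discontinuation or death.
- Long-term, including crossover: "this analysis period starts from the first dose date of mRNA-1273 and continues until the earliest date of" booster dose, study completion, discontinuation or death.
- 28-day period, the primary one for unsolicited AEs: "this stage starts at the day of each vaccination and continue through the earliest date of" the 27th subsequent day or the next vaccination.

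For the original mRNA-1273 group, the pre-booster long-term safety period ends at "Earliest date of booster dose (exclusive), study discontinuation, study completion, death, or data cutoff".

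**The concern.** The exception at the first injection embodies a conservative principle: when the onset is ambiguous, the AE is placed after vaccination. Carried over unchanged, the rule does the reverse for later doses. An AE known only to have started in the booster month goes to the 1st of that month, normally before the booster, and so into the pre-booster period.

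Booster safety is a primary objective (section 2.2.1). Unsolicited AEs, MAAEs, SAEs and AESIs after the mRNA-1273 booster or third dose are primary endpoints (section 3.3.1). For the mRNA-1273.214 booster only safety is analysed (section 6.1). Booster/third-dose safety tables are produced separately (section 6.3.1.1), so an event moved across the dose date leaves them. The error runs towards too few post-dose events.

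**Working it through.** The plan gives no figure to reproduce. The check applies the rule as written.

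**Can the exception ever cover the booster or third dose?** The shortest stated interval is 3 months after Dose 2 (Appendix J, footnote 1, for the mRNA-1273.214 booster; section 4.1.4 of the Part 1/blinded-phase SAP for the third dose). Dose 2 itself follows Dose 1 by about 28 days. The booster or third-dose month is therefore never the first-injection month, and the day-missing exception cannot apply there.

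**Example (assumed dates).** First injection 12 Aug 2021, booster 14 Apr 2022, AE recorded as April 2022, true onset 18 Apr.

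| Rule | Imputed start | Period |
|---|---|---|
| As written | 1 Apr 2022 (13 days before booster) | pre-booster long-term |
| Anchored to booster | 14 Apr 2022 | booster, and 28-day |
| As written, year only known | 1 Jan 2022 | pre-booster |

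The event also leaves the 28-day period altogether. The 1st of the month is at most 30 days before the booster, and Dose 2 was about 90 days or more before it, so the imputed date is about 60 days or more after Dose 2, beyond day 27.

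**Share affected, day missing.** Assumptions: every dose date in a 365-day year and every true onset on days 0-27 after the dose is equally likely.

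- Combinations: 365 × 28 = 10,220.
- Onset in a later calendar month: 1 + 2 + … + 27 = 378 per month, × 12 = 4,536. These are imputed to the 1st of the later month, after the dose, and are kept.
- Onset in the same month: 10,220 − 4,536 = 5,684.
- Of these, dose given on the 1st: 12 × 28 = 336, kept.
- Dated before the dose: 5,684 − 336 = 5,348.
- Shares: 5,348/5,684 = 94% of same-month onsets; 5,348/10,220 = 52% of onsets in days 0-27.

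For days 0-6: 365 × 7 = 2,555; later month 21 × 12 = 252; dose on the 1st 12 × 7 = 84; predated 2,555 − 252 − 84 = 2,219, or 87%.

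With the exception anchored to the dose that opens the period, 0 of 10,220 are dated before it.

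**Year-only dates.** If the AE year is the booster year, the imputed date is 1 January or, when the first injection was in that year and its exception applies, the first-injection date. Both precede the booster unless it was given on 1 January. For onsets in days 0-27, with the first injection in an earlier year, the kept cases are 28 (1 January dose) + 378 (onset in the next year) = 406. The predated share is (10,220 − 406)/10,220 = 96%. Over longer follow-up it is lower: an onset t months after an evenly spread booster falls in the next year with probability t/12. That averages 1/2 over 12 months and 1/4 over 6 months, and those events are kept.

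**Crossover.** Section 6.1 uses the unqualified term for Day 1 when it defines the overall period. In the study-day rule for the Part 2 open-label phase, the same term stands for Crossover Day 1. Section 8.4 does not say which is meant. On the first reading (placebo injection 12 Aug 2021, crossover 10 Dec 2021, AE recorded as December 2021, all assumed), the date becomes 1 Dec, before crossover. On the second it becomes 10 Dec.

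**The case against.** The case for leaving the rule alone has substance. The events are not deleted: they stay treatment-emergent (section 6.3.1), and for the original mRNA-1273 group they appear in the pre-booster long-term period and in the analysis made regardless of booster dose. Partial dates may be few, because booster contacts are scheduled at BD-D8 and BD-D29 and SAEs and AESIs are to be reported within 24 hours of awareness. Suspected myocarditis or pericarditis is adjudicated, and AESIs are listed individually. These points limit the likely size. They do not make the rule right.

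Four stronger readings are tempting, and the documents do not support them:

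- A reader might infer that every partial date ends up before the booster, or that a year-only AE can never count after it. AEs starting in a later month (day missing) or a later year (year only) are imputed after the dose.
- A reader might infer that every day-missing AE in the booster month is misassigned. Some truly began before the dose that month and are placed correctly.
- A reader might infer that crossover participants are certainly affected. That depends on an undefined term; what the text shows is ambiguity.
- A reader might infer that rare AESI counts will change. Nothing indicates that AESI onset dates will be partial.

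Re-anchoring also has a cost. For year-only dates, some AEs that followed Dose 1, Dose 2 or placebo will be attributed to a later dose in the same year.

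**Conclusion.** The rule is wrong as written for the booster and third dose. A day-missing AE that began after the dose in the same calendar month is dated before it unless the dose was given on the 1st. It is then missing from the booster/third-dose and 28-day tables and is counted in the pre-dose period. The 94%, 52% and 87% figures are shares of AEs with a missing day and a true post-dose onset, under even spread of dose dates and onsets; they are not shares of all AEs. Year-only AEs in the booster year are affected likewise, except after a 1 January booster. For crossover the rule fails only if first injection means the first placebo injection. The absolute effect is unknown because the number of partial dates is not given. The direction is anti-conservative for a primary safety analysis.

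**What to change.** In section 8.4 of the open-label/booster SAP:

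1. When the known month and year coincide with those of a booster, third dose or crossover first dose, and the AE end date is on or after that dose or missing, impute the start to that dose date, unless other recorded information shows an earlier onset.
2. Define first injection for crossover participants.
3. For year-only dates, apply the same anchor within the booster/third-dose (or crossover) safety analysis and flag the events. State that some earlier AEs will be conservatively attributed to the later dose.

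Appendix C needs no change. Its Table 5 classes a medication started between the first injection and 28 days after the last as concomitant whichever date is imputed, and an earlier imputed start does not remove an ongoing medication from the post-booster windows.

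The cost is one paragraph of SAP text and a small programming change, with no new data collection.
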